#### 5.1.3 Groups for Comparison

Data will be summarised by RBP-6000 induction arm: RI and SoC induction, and total (where applicable). The treatment labels will be presented in the TLFs as:

- "RI" for rapid induction
- "SoC" for standard of care induction
- "Total" for all (RI + SoC)

Comparison will be made (where applicable) by RBP-6000 induction arms (RI and SoC induction).

Participants may be analysed corresponding to the induction treatment they received ("as treated", ie, actual arm) or corresponding to the induction treatment to which they were randomised ("as randomised", ie, planned arm), as stated in the analysis populations definitions (Section 4) or in sensitivity analysis sections (Section 5.3.3).

#### 5.1.4 Open-label Induction Sub-study Period

The treatment period for the OLIS begins when the first TM BUP dose is given and ends immediately prior to a participant receiving double-blind RBP-6000 Injection 3. Note that predose assessments for Injection 3 are considered part of the OLIS. See Figure 1 for the OLIS schematic.

For the RI arm, the Induction Day 1 Visit of the most recent induction attempt and the Week 1 Day 1 Visit for the first RBP-6000 injection occur on the same calendar day. In the protocol, this day is the "Day 1" of the RI arm: the RI participants receive their first RBP-6000 injection about 1 hour post TM BUP and then remain on site about 4 hours post injection. The investigator-evaluated PWs occurring within the 1-hour window post TM BUP under Induction Day 1 Visit and those occurring within the 4-hour window post RBP-6000 injection under Week 1 Day 1 Visit are recorded on "Day 1" of the RI arm.

[figure not shown]
For the SoC arm, the Week 1 Day 1 Visit for the first RBP-6000 injection occurs about 7 to 14 days after the Induction Day 1 Visit. At the Induction Day 1 Visit (of the most recent induction attempt), the SoC participants remain on site about 5 hours after the first TM BUP, to serve as the control period for the 5-hour on-site duration post TM BUP on "Day 1" of the RI arm; at Week 1 Day 1 Visit, the SoC participants remain on site about 4 hours post RBP-6000 injection at Week 1 Day 1 Visit, to serve as the control period for the 4-hr on-site duration post injection on "Day 1" of the RI arm.

Therefore, the Induction Day 1 Visit or the Week 1 Day 1 Visit will be used to refer to the "Day 1" of the RI arm, depending on which visit of the SoC arm is to be compared.

Handling of multiple Induction Check-in Days/repeat attempts at induction are described in the analysis sections for the individual endpoints. Example scenarios that may result in multiple Induction Check-in Days/repeated attempts at induction are the following:

- PW from TM BUP that would prevent RBP-6000 administration
- Participant must leave before the in-clinic assessments on an Induction Day Visit are completed

Figure 1. Open-label Induction Sub-study Schematic

BUP=buprenorphine; min=minimum; SoC=standard of care; TM=transmucosal

#### 5.1.5 Randomisation Stratification Variable

The OLIS randomisation is stratified according to the same-day UDS result for fentanyl (negative or positive) on the first induction attempt. The same-day UDS result for fentanyl will be recorded in the eCRF, and the randomisation system will utilise the value recorded at the time of randomisation to assign the randomisation stratum. There is a possibility the incorrect stratum is used for randomisation, in the event the same-day UDS result for fentanyl recorded in the eCRF on the first induction attempt is corrected following randomisation. However, the stratum used for randomisation will be used for analyses involving stratum. See Section 5.7.6 for analyses by fentanyl-positive and fentanyl-negative UDS subpopulations, as defined by the eCRF same-day UDS result for fentanyl on the Induction Day 1 Visit of the most recent induction attempt.

#### **5.2** Participant Dispositions

#### 5.2.1 Definitions

Participant completion and discontinuation from treatment are described in the protocol as follows:

- A completed participant for the OLIS is one who has been randomised and has completed Injection 3, otherwise he/she is considered prematurely discontinued. Note that participants who prematurely discontinue from the OLIS will also prematurely discontinue from the main study.
- A participant will be considered withdrawn from treatment if the participant has permanently discontinued study treatment.

#### 5.2.2 Analysis of Participant Disposition

The number and percentage of participants who were screened and randomised or not randomised, and the reasons for not randomised (ie, discontinued before randomisation), will be summarised for the Screened population. For the SRP and SFAS, the number and percentage of participants who received TM BUP; received RBP-6000 Injections 1, 2, and 3; completed the OLIS (as defined in Section 5.2.1); or discontinued before TM BUP, after TM BUP, before RBP-6000 injection, or after RBP-6000 during the OLIS (and the reasons for discontinuation), will be summarised within randomisation strata and for overall. These participant disposition analyses will be repeated for participants who did and did not experience precipitated withdrawal.

The number and percentage of participants comprising each analysis population (Section 4) will be summarised.

The number and percentage of participants failing entry criteria will be summarised overall and by individual criterion for the Screened population and the SRP.

The number and percentage of participants with important (key) protocol deviations will be summarised overall and by investigator site for the SRP.

The number and percentage of participants who were randomised using the incorrect stratum (ie, the stratum the IWRS used for randomisation does not match the stratum data as collected on the eCRF, see Section 5.1.5) will be summarised for the SRP.

#### 5.3 Primary Endpoint Analysis

Refer to Table 2 for the information on the attributes of the primary estimand. Additional details are provided below.

The analyses of primary endpoint will use the Evaluable Population for treatment retention/discontinuation.

#### **5.3.1** Definition of endpoint

Treatment retention at Injection 2 is defined as the proportion of participants receiving Injection 2 at the Week 2 Visit among those in the Evaluable Population for treatment retention/discontinuation.

The analysis value (Yes/No) for treatment retention at Injection 2 for each participant is assigned as described in Table 6 for the Evaluable Population for treatment retention/discontinuation.

Table 6. Assignment of Treatment Retention at Injection 2

Participant status	Treatment Retention at Injection 2
Received Injection 2 at Week 2 (nominal) Visit	Yes
Missed Injection 2 at Week 2 (nominal) Visit but received Injection 3 at Week 6 Day 36 Visit	Yes
Otherwise	No

#### 5.3.2 Main analytical approach

The treatment retention rate at Injection 2 will be estimated by Bayesian beta-binomial model using non-informative uniform prior, ie, Beta (1,1), within individual induction arms. The posterior distribution of retention rate difference between the 2 arms will be obtained and utilised to calculate the posterior probability of NI of the RI to SoC induction using a 10% NI margin or a favourable trend of the RI over the SoC induction.

The criterion for success (ie, demonstrating NI) is based on the posterior probability of retention rate difference (RI - SoC) greater than -10%. The NI of RI will be declared if the posterior probability is at 96% or greater. If the NI of RI to SoC is declared, the posterior possibility of retention rate difference (RI - SoC) greater than 0 will be estimated to evaluate the superiority of RI over SoC induction.

#### 5.3.3 Sensitivity Analysis

The analysis will be repeated, except participants will be analysed as per the randomised treatment (ie, planned arm).

#### 5.4 Secondary Endpoints Analysis

Refer to Table 2 for the information on the attributes of the secondary estimands. Additional details are provided below.

#### 5.4.1 Secondary endpoint 1: Time to treatment discontinuation

The analysis of secondary endpoint 1 will use the Evaluable Population for treatment retention/discontinuation.

#### 5.4.1.1 Definition of endpoints

This analysis will utilise the most recent induction attempt. The time from the first dose of TM BUP to treatment discontinuation will be calculated in days as the date of the last scheduled visit observed during the OLIS minus the date of the first dose of TM BUP (for the most recent induction) +1. Participants receiving RBP-6000 Injection 3 will be censored administratively at the end of the OLIS, and the corresponding censor time will be calculated as the date of Injection 3 minus the date of the first dose of TM BUP +1.

The population for analysis (ie, the at-risk population at time 0) will be the Evaluable Population for treatment retention/discontinuation.

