4.1.2.1 Rapid Induction

The flow of activities for participants in the rapid induction arm is provided in Figure 3.

After completing the pre-TM buprenorphine assessments, participants will then be administered 4 mg of TM buprenorphine.

After a minimum of 1 hour has elapsed since the 4-mg dose of TM buprenorphine was administered, the participant will be re-assessed for withdrawal symptoms (COWS) and tolerability (AEs). Participants must meet **all** of the following criteria to receive RBP-6000 using rapid induction:

- 1. The participant does not display any allergic/hypersensitivity reaction to TM buprenorphine.
- 2. Based on the Investigator's judgment, the participant did not experience precipitated withdrawal symptoms from the most recent TM buprenorphine administration that would prevent RBP-6000 administration.
- 3. Based on the Investigator's judgment, the participant is not sedated (i.e., participant cannot be easily aroused by external stimuli).

After receiving TM buprenorphine, if the participant is sedated or has precipitated withdrawal symptoms that would prevent RBP-6000 administration, in the opinion of the Investigator, the participant may either remain in the clinic to repeat the 4 mg TM buprenorphine later that same day or may return to the site and repeat the induction within 30 days of informed consent.

If the participant is eligible for dosing with RBP-6000, pre–RBP-6000 assessments will be conducted including, but not limited to, vital signs, will be collected. If the participant is eligible, 300 mg RBP-6000 may be administered SC and the visit will be considered Day 1.

Participants will be asked to remain in the clinic for at least 4 hours post-RBP-6000. A COWS assessment will be completed at 1, 2 and 4 hours and an injection site evaluation will be completed at 1 and 2 hours post–RBP-6000.

[figure not shown]
All AEs and concomitant medications should be recorded. If the participant experiences withdrawal symptoms post RBP-6000 on Day 1, the participant may be treated symptomatically (SAMHSA TIP 63 2020; see Section 9.13 for treatment of withdrawal symptoms). Also, following the first injection of 300 mg RBP 6000, TM buprenorphine in increments of 2 to 4 mg up to a maximum dose of 12 mg (inclusive of pre–RBP-6000 TM buprenorphine) may be administered on Day 1 at the discretion of the Investigator to alleviate withdrawal symptoms while on site.

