6.5.1 Open-label Treatment Period

The Open-label Treatment Period (OLTP) begins when the first TM buprenorphine dose is given and ends immediately prior to a participant receiving double-blind RBP-6000 Injection 3. Note that pre-dose assessments for Injection 3 are considered part of the OLTP.

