3. SUB-STUDY ENDPOINTS

The primary endpoint of this sub-study is treatment retention at Injection 2 defined as the proportion of participants receiving Injection 2 at the Week 2 visit among those who received at least 1 dose of TM buprenorphine for induction and did not demonstrate idiosyncratic response to the first dose of TM buprenorphine. Participants who discontinue treatment due to not meeting Inclusion/Exclusion criteria will be excluded.

The secondary endpoints of this sub-study are the following:

- time to treatment discontinuation from the first dose of TM buprenorphine used for induction during the Open-label Treatment Period (OLTP) defined as the number of days from the first dose of TM buprenorphine until the last scheduled visit observed during the OLTP. Participants receiving the third RBP-6000 injection (i.e., the first randomised injection) will be censored administratively at the end of the OLTP; otherwise participants will be viewed as having discontinued treatment at their last scheduled visit observed during the OLTP. Participants discontinued due to idiosyncratic response to the first dose of TM buprenorphine or not met meeting Inclusion/Exclusion criteria will not be included.
- adverse events up to Injection 2, and between Injections 2 and 3

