8.4.2. Sub-study Full Analysis Set

The Sub-study Full Analysis Set (SFAS) will serve as the primary population for the analysis in this sub-study. The SFAS will comprise all participants who are randomised to sub-study treatment and receive the first dose of TM buprenorphine and do not demonstrate idiosyncratic response to the first dose of TM buprenorphine. The participants will be analysed corresponding to the induction arm they received. For analysis pertaining to treatment retention and time-to-treatment discontinuation, the participants who discontinue treatment due to not meeting Inclusion/Exclusion criteria will be excluded. The analysis population for the IA is defined in Section 8.10.

8.5. Primary Endpoint Analysis: Treatment Retention at Injection 2 (received at Week 2 visit)

Retention rate will be estimated by Bayesian beta-binomial model using non-informative uniform prior, i.e., Beta (1,1), within individual induction arms. The posterior distribution of retention rate difference between the 2 arms will be obtained and utilised to calculate the posterior probability of non-inferiority of the rapid induction to SoC induction using a 10% NI margin or a favourable trend of the rapid induction over the SoC induction. The criterion for success (i.e., demonstrating NI) is based on the posterior probability of retention rate difference (rapid – SoC) greater than -10%. The NI of rapid induction will be declared if the posterior probability is at 96% or greater. If the NI is declared, the posterior possibility for superiority of rapid induction over SoC induction will be evaluated.

8.6. Secondary Endpoint Analysis: Time to Treatment Discontinuation from the First Dose of TM Buprenorphine Induction

The time from the first dose of TM buprenorphine to treatment discontinuation will be presented by induction arm using a Kaplan-Meier (KM) curve within the randomisation strata (UDS fentanyl negative vs. positive at the day of first dose of TM buprenorphine) and for overall. Participants receiving the third RBP-6000 injection (i.e., the first

randomised injection) will be censored administratively at the end of the OLTP. Retention rate (with 95% CI) at specific time point will be estimated using KM product limit method for each induction arm. Hazard ratio (with 95% CI) of RBP-6000 rapid induction to SoC induction will be estimated using a Cox proportional hazard model, with arm as a single covariate, stratified by the randomisation strata.

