#### **LIST OF FIGURES**

#### 1 INTRODUCTION

This statistical analysis plan (SAP) provides the detailed methodology for summary and statistical analyses of the efficacy, safety, and pharmacokinetic data collected in the sub-study of Study INDV-6000-401 based on the protocol amendment 3 dated 07 Apr 2022. This document does not modify the plans outlined in the protocol.

The main study is designed to compare the efficacy, safety, and tolerability of 2 maintenance doses of RBP-6000, 300 mg and 100 mg, administered every 4 weeks, in treatment-seeking participants with moderate to severe opioid use disorder (OUD) and high-risk opioid use (ie, those who use opioids via an injection route and/or use high-dose/potency opioids) that may benefit from the higher 300-mg maintenance dose. The Open-label Induction Sub-study (OLIS) is designed to compare the treatment retention of all participants inducted onto RBP-6000 using Standard of Care (SoC) (minimum 7 days of transmucosal [TM] buprenorphine [BUP] per label) with a more rapid induction (RI) onto RBP-6000 treatment. (Note that in the protocol, the OLIS is referred to as the Open-label Treatment Period in the context of the main study.)

The OLIS and main study Schedules of Events can be found in Section 6.3. The duration of participation in the main study is up to approximately 46 weeks (30 days of screening,  $\leq$ 2 weeks of open-label induction, 38 weeks of treatment, and 2 weeks of follow-up). The duration of participation in the sub-study is up to approximately 11 weeks (30 days of screening,  $\leq$ 2 weeks of open-label induction, 5 weeks of treatment).

Specification for tables, listings, and figures (TLFs) will be provided in a separate document.

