## **Development of Statistical Analysis Plan Template**

Table 2. Primary and Secondary Estimands

	Estimand Attributes			
Statistical	Variable/			PLS
Category	Endpoint	Population a	IES	(Analysis)
Primary Obj	ective: To compare treatment retention of partici	pants following rapid induction	or SoC induction of	onto RBP-6000 with respect to:
Primary Efficacy Endpoint	Treatment retention at Injection 2, defined as the proportion of participants receiving Injection 2 at the Week 2 Visit among those who received at least 1 dose of TM BUP for induction and did not demonstrate idiosyncratic response to the first dose of TM BUP. Participants who discontinue treatment within the sub-study due to not meeting Inclusion/Exclusion criteria will be excluded.	Evaluable Population for treatment retention/discontinuation	Not applicable: Intercurrent events are not relevant for this endpoint.	Retention rate will be estimated by Bayesian beta-binomial model using non-informative uniform prior, ie, Beta (1,1), within individual induction arms. The posterior distribution of retention rate difference between the 2 arms will be obtained and utilised to calculate the posterior probability of non-inferiority of the RI to SoC induction using a 10% non-inferiority margin or a favourable trend of the RI over the SoC induction. The participants will be analysed corresponding to the induction regimen used ("as treated" b ).
Primary Efficacy Endpoint/ Sensitivity Analysis	As primary	As primary	As primary	As primary. The participants will be analysed corresponding to the induction arm to which they were randomised ("as randomised" ').
Secondary Endpoint 1	Time to treatment discontinuation from the first dose of TM BUP used for induction during the OLIS, defined as the number of days from the first dose of TM BUP from the most recent induction attempt until the last scheduled visit observed during the OLIS.	As primary	Not applicable: Intercurrent events are not relevant for this endpoint.	KM curve presented by the induction arm within the randomisation strata (UDS fentanyl negative vs. positive at the day of first dose of TM BUP) and overall. Participants receiving Injection 3 will be censored administratively at the end of the OLIS; otherwise, participants will be viewed as having discontinued treatment at their last scheduled visit observed during the

Table 2. Primary and Secondary Estimands

	Estimand Attributes				
Statistical	Variable/			PLS	

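### Secondary endpoint 1: the SAP moves time zero from the first TM buprenorphine dose to the most recent induction attempt and does not declare the change

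*SAP*

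**What the plan says.** **Protocol.** Appendix 22.9, Section 3, gives the endpoint as "defined as the number of days from the first dose of TM buprenorphine until the last scheduled visit observed during the OLTP". The analysis text in Appendix 22.9, Section 8.6, keeps that origin: "The time from the first dose of TM buprenorphine to treatment discontinuation will be presented by induction arm". Section 6.5.1 anchors the period the same way: "The Open-label Treatment Period (OLTP) begins when the first TM buprenorphine dose is given". No passage restarts the clock at a repeat induction. Repeats after a TM dose are foreseen, however. Under Section 4.1.2.1 a rapid-arm participant may have a second dose later the same day, or "may return to the site and repeat the induction within 30 days of informed consent".

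**SAP.** Table 2 has the endpoint "defined as the number of days from the first dose of TM BUP from the most recent induction attempt". Section 5.4.1.1 opens with "This analysis will utilise the most recent induction attempt" and ties the event-time formula to the latest induction in a parenthesis. The next sentence says "the corresponding censor time will be calculated as the date of Injection 3 minus the date of the first dose of TM BUP +1", without that parenthesis.

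**Declared changes.** SAP Section 1 states: "This document does not modify the plans outlined in the protocol". Appendix 6.2 does list departures from the protocol. For this endpoint its only entry is an added exploratory approach, and the time origin is not mentioned.

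**The concern.** Whether and when someone is re-inducted is decided after randomisation, and only people still in the study can be re-inducted. Starting the clock there discards days for which a repeater had already been retained. The Kaplan-Meier (KM) curves, the 35-day retention estimates and the Cox hazard ratio would all use that origin. If later-day repeats are more common in one arm, the shift falls unevenly across the comparison.

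The two sentences of Section 5.4.1.1 also leave a programmer to guess. Following each formula literally gives a repeater who discontinues one origin and a repeater who reaches Injection 3 another.

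**Working it through.** **1. Effect on one participant.** Let g be the days from the first TM dose to the first dose of the latest attempt. Take a rapid-arm participant with g = 7 who receives Injection 1 on the day of the repeat. Use the nominal visit days in protocol Appendix 22.4 and the SAP's +1 convention.

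| Outcome | Protocol origin | SAP origin | SAP formula taken literally |
|---|---|---|---|
| Last scheduled visit Week 3 (Day 15), then discontinued | 15 + 7 = 22 | 15 | 15 |
| Receives Injection 3 (Day 36), censored | 36 + 7 = 43 | 36 | 43 |

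The event time always loses g days. Taken literally, the censoring time keeps them. Both formulas use dates, so a same-day repeat has g = 0 and all three columns agree. Because the repeat window runs from consent, g approaches 30 days only if the first attempt is close to consent and the repeat close to the end of the window.

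**2. Effect on 35-day retention.** Assumptions, none of them in the documents: constant discontinuation of 8% per week; a fraction f of the rapid arm repeating after g days; no later-day repeats in the SoC arm.

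- SAP origin, a repeater retained 35 days from the repeat: 0.92^5 = 0.659.
- Protocol origin, a repeater already retained g days: 0.92^((35 − g)/7). For g = 7 this is 0.92^4 = 0.716. For g = 10 it is 0.92^(25/7) = 0.742.
- Shift in the arm estimate = f × difference. With f = 0.10 and g = 7: 0.10 × (0.716 − 0.659) = 0.0057, about 0.6 points. With f = 0.25 and g = 10: 0.25 × (0.742 − 0.659) = 0.021, about 2.1 points.

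The SAP origin gives the lower rapid-arm figure.

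**3. Simulation on separate assumptions.** This used 326 rapid and 163 SoC participants (489 split 2:1). It assumed that 30% discontinue before Injection 3, spread over visits; that 5%, 10% or 20% of the rapid arm repeat after 1, 7, 14 or 28 days; and that there are no SoC repeats. There were 40 replicates per scenario.

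| Gap | Rapid-arm 35-day KM, protocol origin (5% / 10% / 20% repeating) | SAP origin |
|---|---|---|
| 1 day | 70.4 / 70.4 / 70.4% | 70.4% |
| 7 days | 70.8 / 71.0 / 71.6% | 70.4% |
| 14 days | 71.1 / 71.6 / 72.9% | 70.4% |
| 28 days | 71.7 / 72.8 / 75.2% | 70.4% |

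The largest gap is 0.7518 − 0.7044 = 0.047, or 4.7 points. It needs one in five of the rapid arm to repeat four weeks later, an extreme case given the 30-day window. The simulated hazard ratio (rapid to SoC) was 1.24 on the SAP origin and 1.14 to 1.24 on the protocol origin. Mixing the origins as literally written gave 1.18 to 1.24, with 35-day KM the same as on the single SAP origin. Only the movement in the hazard ratio matters here: its level reflects the assumed 7 to 14 day SoC run-in.

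**4. Fit with the rest of the SAP.** Section 5.1.4 starts the sub-study treatment period at the first TM dose. Section 5.1.5 takes the randomisation stratum from the first induction attempt. Section 5.4.2.1 uses the first dose across all attempts for adverse events. Section 5.4.1.1 can therefore time a participant from a later attempt while stratifying on the first.

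**The case against.** **One clock was intended.** The opening sentence of Section 5.4.1.1 covers the whole analysis, and Table 2 names the most recent attempt. A reader might infer from the censoring sentence that the SAP deliberately runs events and censoring on different clocks. The documents do not support that: a qualifier given one sentence earlier has most likely been dropped. Nor does the omission do much at the landmark, because Injection 3 is nominally Day 36. The wording still needs correcting, since the unqualified phrase means the first dose across all attempts in Section 5.4.2.1.

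**Repeats are not confined to one arm.** A reader might also infer that the lost time falls mostly in the rapid arm. No counts support this. SAP Section 5.1.4 refers to a most recent attempt for SoC participants and gives leaving before assessments are complete as a general example. Section 5.6.1 summarises attempts for both arms. What stands is narrower: the protocol sets out the return-and-repeat option after a TM dose in rapid-arm text, so an imbalance is plausible but of unknown size.

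**The effect is small and no event status changes.** With 326 rapid participants and retention near 66%, the standard error is √(0.66 × 0.34 / 326) = 0.026 and the 95% half-width about 5 points, so 0.6 to 2.1 points lies well inside it. Someone who fails a first attempt and never returns still counts as an event. Both statements are right, and they limit the point's importance. They do not justify an avoidable, undeclared shift.

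**The SAP origin is defensible.** Starting at the attempt that led to treatment avoids counting time around a failed attempt as retention, and the protocol does not discuss repeats for this endpoint. That argues for reporting this version too. But the protocol's wording and its definition of the open-label period both point to the first dose. Declaring the change would cure the silence, not the post-randomisation origin.

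**Conclusion.** The point holds. For secondary endpoint 1 the SAP replaces the protocol's time origin with a post-randomisation one and does not list the change. The missing qualifier in the censoring formula is a lesser drafting fault.

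The consequence is modest. Only participants re-inducted on a later day are affected. On the assumptions in step 2, rapid-arm 35-day retention is 0.6 to 2.1 points lower than on the protocol origin; it is unchanged if all repeats are same-day. The wider simulated range of 0 to 4.7 points rests equally on assumed repeat rates and gaps. Retention at Injection 2, the completion-rate analysis in SAP Section 5.4.1.3, the sample size and the power do not use this clock. The change should be made, but nothing in the primary non-inferiority conclusion turns on it.

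**What to change.** - In SAP Table 2 and Section 5.4.1.1, define time zero as the first TM buprenorphine dose after randomisation, and write that origin into both the event and the censoring formula.
- Keep the most-recent-attempt version as a named sensitivity analysis, again with one origin in both formulas.
- List that sensitivity analysis in Appendix 6.2.

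The cost is SAP wording and one extra run of the KM and Cox analyses. No new data are needed: the formulas use dosing and visit dates, and the SAP already uses the first dose across all attempts for adverse events.
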